10.3.4. Pharmacokinetic/Pharmacodynamic Analyses	44
10.3.5. Evaluation of Immunogenicity	44
10.3.6. Data Review During the Study	45
10.3.7. Interim Analyses	45
11. References	47

List of Tables

Table		Page
Table GPGG.1.	Objectives and Endpoints	16
Table GPGG.2.	Subject Groups based on Renal Impairment Status	17
Table GPGG.3.	Renal Function Classification for Primary Analyses	44

List of Figures

Figure		Page
Figure GPGG.1.	Illustration of study design for Groups 1 to 4	18
Figure GPGG.2.	Illustration of study design for Group 5.	19
Figure GPGG.3.	Interim data review decision tree.	46

List of Appendices

Appendix		Page
Appendix 1.	Abbreviations and Definitions	49
Appendix 2.	Clinical Laboratory Tests.....	52
Appendix 3.	Study Governance, Regulatory and Ethical Considerations	53
Appendix 4.	Hepatic Monitoring Tests for Treatment-emergent Abnormality.....	56
Appendix 5.	Blood Sampling Summary.....	57
Appendix 6.	Pancreatic Monitoring	58
Appendix 7.	Permitted Concomitant Medication.....	60
Appendix 8.	Calculation of Estimated Glomerular Filtration Rate.....	61
Appendix 9.	Protocol Amendment I8F-MC-GPGG(b) Summary Pharmacokinetics of LY3298176 Following Administration to Subjects with Impaired Renal Function.....	62

1. Protocol Synopsis

Title of Study:

Pharmacokinetics of LY3298176 Following Administration to Subjects with Impaired Renal Function

Rationale:

LY3298176 is a balanced glucose-dependent insulinotropic polypeptide and glucagon-like peptide-1 receptor co-agonist being developed as a weekly treatment of hyperglycemia in patients with type 2 diabetes mellitus (T2DM). Renal failure is a common sequelae of diabetes; it is therefore important to understand the influence of differing degrees of renal impairment on the pharmacokinetics (PK) of LY3298176.

Objectives/Endpoints:

Objectives	Endpoints
Primary To estimate the PK parameters of LY3298176 in subjects with mild, moderate, or severe renal impairment, and in subjects with ESRD after a single 5-mg SC dose of LY3298176 compared to control subjects with normal renal function.	
 LY3298176 PK parameters, including $AUC_{0-\infty}$, $AUC_{0-t_{last}}$, and C_{max}
Secondary To assess the tolerability of LY3298176 in subjects with mild, moderate, or severe renal impairment, and in subjects with ESRD after a single 5-mg SC dose of LY3298176 compared to control subjects with normal renal function.	
 Adverse events

Abbreviations: $AUC_{0-\infty}$ = area under the concentration versus time curve from time zero to infinity; $AUC_{0-t_{last}}$ = area under the concentration versus time curve from time zero to the time of last measured concentration; C_{max} = maximum drug concentration; ESRD = end-stage renal disease; PK = pharmacokinetic; SC = subcutaneous.

Summary of Study Design:

Study I8F-MC-GPGG is a Phase 1, multicenter, nonrandomized, open-label, parallel-design study in subjects with mild, moderate, or severe renal impairment, or end-stage renal disease (ESRD), and control subjects with normal renal function. Renal function will provide the basis for assignment to treatment group.

- Group 1: control subjects with normal renal function (estimated glomerular filtration rate [eGFR] ≥ 90 mL/min/1.73m²)
- Group 2: subjects with mild renal impairment (eGFR between 60 and 89 mL/min/1.73m²)
- Group 3: subjects with moderate renal impairment (eGFR between 30 and 59 mL/min/1.73m²)
- Group 4: subjects with severe renal impairment (eGFR <30 mL/min/1.73m² and not requiring dialysis)
- Group 5: subjects with ESRD (have received dialysis for at least 3 months).

Subjects with T2DM and renal impairment will be permitted to enroll in the study. Subjects with T2DM will not be included in Group 1.

Treatment Arms and Planned Duration for an Individual Subject:

Subjects will be screened over a 28-day period prior to dosing. Subjects will be admitted to the clinical research unit (CRU) on Day -1, receive a single subcutaneous injection of LY3298176 on Day 1, remain at the CRU until discharge on Day 5, and return to the CRU on Days 8 and 15 for PK blood sampling and other study procedures. Subjects will also return to the CRU for a follow-up visit at least 28 days postdose for final PK and study assessments.

Subjects will receive either 5 mg LY3298176 or, depending on interim analysis results, a dose of LY3298176 reduced by approximately 50%.

Number of Subjects:

Approximately 58 subjects will be enrolled so that approximately 48 subjects complete the study, such that approximately 8 subjects per group complete Groups 2 through 5. Approximately 16 completers are needed from Group 1 in order to facilitate demographic matching with the subjects in other groups.

Statistical Analysis:

Pharmacokinetics: The primary parameters for analysis are area under the concentration versus time curve (AUC) from time zero to infinity ($AUC_{0-\infty}$), AUC from time zero to the time of last measured concentration ($AUC_{0-t_{last}}$), and maximum drug concentration (C_{max}); log transformation will be applied. An analysis of variance model with subject group as fixed factor will be used in the main analyses. The 90% confidence interval of the ratio between each impaired renal function group versus the control group will be estimated. Additional supportive analysis is the evaluation of the relationship between the PK of LY3298176 and mean eGFR, as determined by the Modification of Diet in Renal Disease abbreviated equation. Scatter plots of PK parameter versus eGFR will be produced and analyzed using either a mixed-effects linear or a nonlinear regression approach with eGFR as a continuous covariate on PK parameters.

Safety: Descriptive statistics will be used to summarize safety parameters.

2. Schedule of Activities

Study Schedule Protocol I8F-MC-GPGG

	Screening	Study Days									Follow-up or ED	Comments
Procedure	Days -28 to -1	Day -1	Day 1	Day 2	Day 3	Day 4	Day 5	Day 8	Day 15	Day ≥28		
Informed Consent	X											
Subject Admission to CRU		X										
LY3298176 Administration			X									Study drug will be administered after an overnight fast of at least 8 hours.
Subject Discharge from CRU							X					Subjects may stay longer at the investigator's discretion.
Outpatient Visit								X	X	X		
Medical History	X											
Physical Examination	X	X						X	X	X		After screening, medical assessment only performed to include medical review and targeted examination, as appropriate.
Weight	X	X								X		
Height	X											
Temperature	X	X										
Urine Drug Screen	X	X						X	X			
Ethanol Testing		X						X	X			
Safety 12-lead ECG (hours)	X		Predose		48		X			X		Single ECG will be collected. ECGs must be recorded before collecting any blood samples. Subjects must be supine for approximately 5 to 10 minutes before ECG collection, and remain supine but awake during ECG collection.
Supine Vital Signs (hours)	X	X	Predose, 12	24	48	72	96	168	336	X		Time points may be added, if warranted and agreed upon between Lilly and the investigator.
Clinical Laboratory Tests	X	X			X		X	X	X	X		See Appendix 2 for details.
Estimated Glomerular Filtration Rate	X	X										
Pregnancy Test	X	X						X	X			Female subjects only. See Appendix 2 for details.
AEs/Concomitant Medications	X	X	X	X	X	X	X	X	X	X		
Pharmacogenomic Sample			Predose									Single sample for pharmacogenetic analysis.

Procedure	Screening	Study Days									Follow-up or ED	Comments
		Day -28 to -1	Day -1	Day 1	Day 2	Day 3	Day 4	Day 5	Day 8	Day 15		
Anti-LY3298176 Antibodies (hours)			Predose							336	X	Time-matched PK sample should be collected at each time point. In the event of drug hypersensitivity reactions (immediate or non-immediate), samples will be collected as close to event onset as possible, at event resolution, and 30 days following the event. Subjects with TE ADA at follow-up/ED will undergo additional follow-up. See Section 9.6.1 for details.
Glucose Monitoring (hours)			Predose, 12	24	48	72	96	168	336		X	Performed using a bedside glucose monitor. Additional measurements may be taken at the discretion of the investigator as clinically indicated.
PK Sampling (hours)			Predose, 8, 12	24	48	72	96	168	336		X	Up to a 10% deviation from the nominal collection time is permissible.
Assessment of Injection-site Reactions (hours)			Predose, 0, 6, 12	24	48							0-hour assessment should be performed within approximately 5 minutes after subcutaneous injection. Additional assessments may be performed if deemed necessary by the investigator.

Abbreviations: AE = adverse event; CRU = clinical research unit; ECG = electrocardiogram; ED = early discontinuation; PK = pharmacokinetic(s);

T2DM = type 2 diabetes mellitus; TE ADA = treatment-emergent antidrug antibodies.

Note: All sampling times are given relative to dosing with LY3298176 (predose or hours postdose).

Note: If multiple procedures take place at the same time point, the following order of the procedures should be used: ECGs, vital signs, clinical laboratory sample, and PK sample, with PK sampling time the priority.

3. Introduction

3.1. Study Rationale

Study I8F-MC-GPGG is a Phase 1, multicenter, nonrandomized, open-label, parallel-design study in subjects with mild, moderate, or severe renal impairment, or end-stage renal disease (ESRD), and control subjects with normal renal function.

LY3298176 is currently being investigated for its use in the treatment of hyperglycemia in patients with type 2 diabetes mellitus (T2DM). Renal failure is a common sequelae of diabetes; it is therefore important to understand the influence of differing degrees of renal impairment on the pharmacokinetics (PK) of LY3298176. The primary purpose of this study is to determine the PK of a single subcutaneous (SC) dose of LY3298176 in subjects with renal impairment compared to subjects with normal renal function. The results of this study will be used to support appropriate dose recommendations in patients with T2DM with varying degrees of renal impairment.

3.2. Background

In normal physiology following a meal, the incretins glucagon-like peptide-1 (GLP-1) and glucose-dependent insulinotropic polypeptide (GIP) are secreted from enteroendocrine cells in the gut to enhance the physiological responses to food intake, including insulin secretion, nutrient disposal, and the sensation of satiety. It is now well established that T2DM patients have impaired incretin responses (Nauck et al. 2004), and pharmacologic interventions providing either GLP-1 receptor agonistic peptides or dipeptidyl peptidase (DPP)-IV inhibitors (which delay degradation of endogenous GIP and GLP-1) are successfully used in the treatment of T2DM (Drucker and Nauck 2006; Amori et al. 2007; Baynes 2010). Although GLP-1 is regarded as the incretin of therapeutic utility in T2DM patients, published data demonstrates that overexpression of GIP may lead to improved body weight and glycemic control, and the combination of GLP-1 and GIP may result in improved glycemic efficacy and weight management compared with GLP-1 agonists alone (Kim et al. 2012; Finan et al. 2013).

LY3298176 is a long-acting, dual incretin receptor co-agonist that binds to both the GIP receptor and the GLP-1 receptor. LY3298176 consists of a peptide component based on the GIP sequence. **CCI** [REDACTED]

The unique co-agonist properties of LY3298176 allow for pharmacological effects to be realized at metabolically active tissues (such as pancreatic β -cells and adipose tissue) that express both GIP and GLP-1 receptors. This could maximize the intended therapeutic benefit of increased energy utilization and greater weight loss while also improving glycemic control in patients with T2DM (Baggio and Drucker 2007).

The safety, tolerability, and PK/pharmacodynamics of LY3298176 were evaluated in a 3-part, Phase 1 clinical pharmacology trial, I8F-MC-GPGA (GPGA) in healthy subjects and patients with T2DM. In Study GPGA, LY3298176 was administered by SC injection as a single dose of 0.25 to 8 mg to healthy subjects (Part A); as multiple doses of 0.5 to 10 mg to healthy subjects (Part B); and as multiple doses of 0.5 to 15 mg administered to patients with T2DM (Part C).

Following administration of a single dose of LY3298176, the maximum drug concentration (C_{max}) was observed to occur between 8 and 96 hours. The mean terminal half-life was approximately 5 days, thus supporting a QW dosing regimen. Pharmacokinetic data from the Phase 1 study supports apparent dose-proportionality of LY3298176.

Based on preliminary data, 52 subjects (out of 142 subjects dosed in this study) received 4.5 mg (6 healthy subjects) to 5 mg as a single dose or as the first dose (32 T2DM out of 47 subjects). There were no reported LY3298176-related SAEs.

Overall, gastrointestinal events (eg, vomiting, abdominal distension, nausea, diarrhea) were the most frequently reported adverse events (AEs). These AEs increased in number and severity with increasing doses, and higher doses appeared to be better tolerated when LY3298176 was administered via dose titration. The reported gastrointestinal- (GI-) related AEs are consistent with GLP-1 pharmacology and those observed previously following administration of GLP-1 receptor agonists (RAs) (Nauck et al. 2009; Dungan et al. 2014; Giorgino et al. 2015; Jendle et al. 2016; Nauck et al. 2016).

In Part A (SAD) of Study GPGA, with increasing doses there was an increase in the number and severity of AEs related to LY3298176. At the 5-mg dose, 6 subjects reported a total of 23 AEs that were all mild in severity. At the 8-mg dose, 7 subjects reported a total of 31 AEs, 21 of which were mild and 10 moderate in severity. Two of 6 subjects who received the 5-mg dose reported 5 mild AEs of vomiting and 1 subject reported a mild AE of nausea, whereas at the 8-mg dose, 3 of 7 subjects reported 12 episodes of vomiting, and 4 of 7 subjects reported 4 AEs of nausea. Two subjects who received 8 mg as a single dose and reported AEs of vomiting and nausea required treatment with antiemetics and IV fluids. Further dose escalation was stopped and the 5-mg dose was considered the maximum tolerated dose.

Based on preliminary data from Study GPGA, the most commonly observed cardiovascular changes included increased heart rate. Consistent with other GLP-1 RAs, dose-dependent increases in pulse rate were observed with administration of LY3298176 in healthy subjects and patients with T2DM. In Part A, the largest least squares (LS) mean time-averaged pulse rate change from baseline to 168 hours compared to placebo was an increase of 8.42 bpm for the single 8-mg dose group. For the multiple dose groups, the largest LS mean increases in pulse rate compare to placebo for the time-averaged change from baseline to 72 hours were 5.24 bpm in the 10-mg titration dose group in Part B, and 10.28 bpm in the 15-mg titration dose group in Part C. However, the increases did not result in any subject discontinuations. There were no clinically significant changes in systolic or diastolic blood pressure (BP) or QT/corrected QT (QTc) interval prolongation observed in either healthy subjects or patients with T2DM.

3.3. Benefit/Risk Assessment

Preclinical data and the preliminary clinical data (see Section 3.2) from Study GPGA support further clinical development for LY3298176.

No clinically significant safety or tolerability concerns were identified up to the highest single-dose level of 8 mg or following 4 QW doses titrated up to 15 mg in Study GPGA. Based on this information, 5 mg doses to be administered in Study GPGG are reasonably anticipated to be tolerable in subjects with renal impairment and in control healthy subjects. Subjects will reside in the clinical research unit (CRU) under close monitoring for at least 5 days, with the option of being kept for longer; discharge from the CRU will be per investigator discretion. An interim analysis safety, tolerability, and PK data is planned to determine whether dose adjustments are needed (see Section 10.3.7).

For safety purposes, blood glucose levels will be monitored for all subjects. Section 9.4.3.1 describes glucose monitoring procedures and how episodes of hypoglycemia or hyperglycemia will be treated, if necessary.

Any identified potential risks are similar with the risks associated with currently available long-acting GLP-1 RAs (see Section 3.2), are considered to be manageable, and are able to be monitored.

There is no anticipated therapeutic benefit for the subjects in this study.

More information about the known and expected benefits, risks, serious AEs (SAEs), and reasonably anticipated AEs of LY3298176 are to be found in the Investigator's Brochure (IB).

4. Objectives and Endpoints

Table GPGG.1 shows the objectives and endpoints of the study.

Table GPGG.1. Objectives and Endpoints

Objectives	Endpoints
Primary To estimate the PK parameters of LY3298176 in subjects with mild, moderate, or severe renal impairment, and in subjects with ESRD after a single 5-mg SC dose of LY3298176 compared to control subjects with normal renal function.	
 LY3298176 PK parameters, including $AUC_{0-\infty}$, $AUC_{0-t_{last}}$, and C_{max}
Secondary To assess the tolerability of LY3298176 in subjects with mild, moderate, or severe renal impairment, and in subjects with ESRD after a single 5-mg SC dose of LY3298176 compared to control subjects with normal renal function.	
 Adverse events
Exploratory To evaluate the formation of ADA to LY3298176 after a single 5-mg SC dose administered to subjects with mild, moderate, or severe renal impairment, and in subjects with ESRD.	
 Presence of ADA to LY3298176

Abbreviations: ADA = antidrug antibodies; $AUC_{0-\infty}$ = area under the concentration versus time curve from time zero to infinity; $AUC_{0-t_{last}}$ = area under the concentration versus time curve from time zero to the time of last measured concentration; C_{max} = maximum drug concentration; ESRD = end-stage renal disease; PK = pharmacokinetic; SC = subcutaneous.

5. Study Design

5.1. Overall Design

This is a Phase 1, parallel-design, open-label, multicenter, single-dose study to assess PK and tolerability of a single dose of LY3298176 in subjects with mild, moderate, or severe renal impairment, or ESRD, and control subjects with normal renal function. Control Group 1 will be healthy subjects with normal renal function. Subjects with T2DM will not be included in Group 1. Subjects with T2DM and renal impairment will be permitted to enroll in Groups 2 to 5, whereas subjects with T2DM and normal renal function will not be permitted. Subjects will be assigned to 1 of 5 groups (Groups 1 to 5) based on criteria outlined in [Table GPGG.2](#). For description of enrollment order and interim analysis, see Section [10.3.7](#). Estimated glomerular filtration rate (eGFR) will be determined by the Modification of Diet in Renal Disease (MDRD) abbreviated equation ([Appendix 8](#)) using serum creatinine levels obtained at Screening and on Day -1; subjects will be assigned to groups based on values from Day -1. See Sections [5.2](#) and [10.1](#) for sample size information.

The control subjects (Group 1) will be selected in order that the mean and distribution of Group 1 are comparable to the mean and distribution for each group with renal impairment (Groups 2 through 5) for age (± 10 years), sex, race, weight (± 10 kg), and body mass index (BMI) ($\pm 20\%$), as far as is practically possible (additional information will be provided to the investigators in a separate document) (FDA 2010). An effort will be made to enroll control subjects that are representative of the races of the impaired subjects. One-to-one matching of subjects (1 impaired subject matched to 1 healthy subject in 1 or more impairment groups using the same criteria previously described) may be used to facilitate interim analysis.

Table GPGG.2. Subject Groups based on Renal Impairment Status

	Classification	eGFR (mL/min/1.73m ²)
Group 1	Control (normal renal function)	≥ 90
Group 2	Mild renal impairment	60-89
Group 3	Moderate renal impairment	30-59
Group 4	Severe renal impairment	<30 and not requiring dialysis
Group 5	End-stage renal disease	Requiring dialysis

Abbreviations: eGFR = estimated glomerular filtration rate (as determined by the Modification of Diet in Renal Disease abbreviated equation).

[figure not shown]
[Figure GPGG.1](#) and [Figure GPGG.2](#) illustrate the study design.

Subjects will visit the CRU to sign the informed consent document and undergo screening procedures up to 28 days prior to dosing.

Subjects will be admitted to the CRU on Day -1. Subjects will be administered a single dose of LY3298176 on Day 1 and will remain in the CRU until after assessments are completed on Day 5. Subjects will return for study visits on Days 8 and 15 and for a final follow-up visit at least 28 days postdose. Clinical laboratory tests, physical examination, vital signs, 12-lead electrocardiograms (ECGs), injection-site reactions, glucose monitoring, AEs, and antidrug antibodies (ADA) will be monitored to assess safety and tolerability. Blood samples for PK and immunogenicity analysis will be collected predose through the final follow-up visit.

[figure not shown]
For subjects with ESRD, administration of LY3298176 should occur at least 24 hours prior to the next planned dialysis session. The time and dates of dialysis sessions from the session immediately prior to dose through Day 8 will be recorded in the case report form (CRF). To eliminate potential variation between different types of dialysis membrane, only high-flux polysulfone membranes will be used.

Study governance considerations are described in detail in [Appendix 3](#).

Abbreviations: ADA = antidrug antibodies; D = Day; PK = pharmacokinetic.

Figure GPGG.1. Illustration of study design for Groups 1 to 4.

† The first postdose dialysis session should be scheduled to start at least 24 hours after administration of LY3298176. Subsequent dialysis sessions should be scheduled as clinically appropriate.

Abbreviations: ADA = antidrug antibody; D = Day; PK = pharmacokinetic.

Figure GPGG.2. Illustration of study design for Group 5.

5.2. Number of Participants

Approximately 58 subjects will be enrolled so that approximately 48 subjects complete the study, such that approximately 8 subjects per group complete Groups 2 through 5 (EMEA CHMP 2016). Approximately 16 completers are needed from Group 1 in order to facilitate demographic matching with the subjects in other groups.

For purposes of this study, a subject is considered to have completed the study when all scheduled procedures shown in the Schedule of Activities (Section 2) have been finished.

5.3. End of Study Definition

End of the study is the date of the last visit or last scheduled procedure shown in the Schedule of Activities (Section 2) for the last subject.

5.4. Scientific Rationale for Study Design

A comprehensive range of renal impairment is necessary to fully characterize the impact of renal impairment on the PK of LY3298176. Subjects undergoing dialysis (Group 5) will be included to determine the effect of dialysis on drug removal.

This study has been designed in accordance with the current regulatory guidances (EMEA CHMP 2016; FDA 2010) for the study of PK in subjects with impaired renal function.

LY3298176 has shown linear and dose-proportional PK, based on preliminary SAD and MAD data in the Phase 1 Study GPGA. Per FDA guidance “a single-dose study is satisfactory for cases where there is clear prior evidence that single-dose studies accurately describe the PK for the drug and potentially active metabolites” (FDA 2010). This renal impairment study will be conducted as a single-dose study.

This study will be open-label. As the primary endpoints are objective rather than subjective, investigators and subjects do not need to be blinded.

Based on the molecular weight of LY3298176, its PK may be impacted by renal impairment. However, LY3298176 is expected to bind to albumin (because of the C20 fatty acid conjugation structure), thus systemically resulting in a larger molecular size and decreasing the likelihood that PK will be meaningfully impacted by renal impairment. Thus the same dose of LY3298176 is planned to be administered to subjects in all groups.

An interim analysis each are planned following dosing of at least 2 subjects in Groups 2 and 3 and appropriate matched-control subjects in Group 1, and following dosing of at least 2 subjects in Groups 4 and 5 and appropriate matched-control subjects in Group 1. An additional interim analysis will be done after completion of the Group 3 (see Section 10.3.7). The purpose of the interim review(s) is to determine the dose level(s) for subsequent subjects, based on safety, tolerability, and PK data. The dose of LY3298176 for subsequent subjects (any or all groups) may be adjusted accordingly after each interim. Data from the additional interim (completion of Group 3) will support Phase 3 enrollment.

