9.5. Pharmacokinetics

At the visits and times specified in the Schedule of Activities (Section 2), venous blood samples of approximately 3 mL each will be collected to determine the plasma concentrations of LY3298176. A maximum of 3 samples may be collected at additional time points during the study if warranted and agreed upon between both the investigator and sponsor. Instructions for the collection and handling of blood samples will be provided by the sponsor. The actual date and 24-hour clock time of each sampling will be recorded.

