Appendix 5. Blood Sampling Summary

This table summarizes the approximate number of venipunctures and blood volumes for all blood sampling (screening, safety laboratories, and bioanalytical assays) during the study.

Protocol I8F-MC-GPGG Sampling Summary

Purpose	Blood Volume per Sample (mL)	Number of Blood Samples	Total Volume (mL)
Screening tests ^a	45	1	45
Clinical laboratory tests ^a	12	5	60
Pharmacokinetics ^a	3	13	26
Immunogenicity ^a	10	3	30
Pharmacogenetics	10	1	10
Glucose monitoring ^a	0.5	9	4.5
Total			175.5
Total for clinical purposes rounded up to nearest 10 mL			180

^a Additional samples may be drawn if needed for safety purposes.

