9.3.2 Pharmacokinetic Statistical Methodology

The main analysis is the evaluation of log-transformed $AUC(0-\infty)$, $AUC(0-t_{last})$, and C_{max} using an analysis of variance model with subject group as a fixed factor. The 90% confidence interval of the ratio between each impaired renal function group versus the control group will be estimated.

Example SAS code:

```
proc mixed data=DATA;
  class group;
  model log_pk = group / ddfm=kr;
  lsmeans group / pdiff cl alpha=0.1;
  ods output lsmeans=lsmeans;
  ods output diffs=diffs;
run;
```

The above analyses will be conducted twice, using different renal function group assignments (eGFR or creatinine clearance [CLcr] based on Day -1 measurements) (Table 2). The analysis based on CLcr will be exploratory.

Table 2. Renal Function Classification for Primary and Exploratory Analyses

Group	Classification	eGFR (mL/min/1.73m ²) ^a	CLcr (mL/min) ^b
1	Control (normal renal function)	≥90	≥90
2	Mild renal impairment	60-89	60-89
3	Moderate renal impairment	30-59	30-59
4	Severe renal impairment	15-29	15-29
5	End-stage renal disease	Requiring dialysis	Requiring dialysis

Abbreviations: CLcr = creatinine clearance; eGFR = estimated glomerular filtration rate.

^a Per enrollment classification; eGFR will be calculated using the Modification of Diet in Renal Disease abbreviated equation.

^b CLcr will be calculated using the Cockcroft-Gault formula (Cockcroft and Gault 1976).

The supporting additional analysis is the evaluation of the relationship between the PK of LY3298176 and mean eGFR, as determined by the MDRD abbreviated equation. Scatter plots of PK parameter versus eGFR will be produced and analyzed using either a mixed-effects linear or a nonlinear regression approach with eGFR as a continuous covariate on PK parameters.

t_{max} will be analyzed using a Wilcoxon rank sum test.

If a dose adjustment after interim is needed, descriptive statistics for the PK parameters will be summarized by dose and subject groups. Dose normalization or other methods may be employed for statistical analyses.

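### Group 5 is included to determine how much drug dialysis removes, but no sample timing, endpoint or planned analysis measures removal

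*Protocol*

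**What the plan says.** Protocol section 5.4 gives one reason specific to Group 5: "Subjects undergoing dialysis (Group 5) will be included to determine the effect of dialysis on drug removal".

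The provisions that bear on it are these:

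- **Dialysis conduct (Protocol 5.1; repeated in SAP section 5).** For ESRD subjects, "administration of LY3298176 should occur at least 24 hours prior to the next planned dialysis session". Later sessions follow clinical need. Session dates and times "from the session immediately prior to dose through Day 8 will be recorded". One membrane type is required, to limit variation between membranes.
- **PK sampling (Protocol section 2).** All groups share one schedule: predose, 8, 12, 24, 48, 72, 96, 168 and 336 h, and follow-up at Day 28 or later. The note under the schedule sets all times by reference to the dose. On timing, "Up to a 10% deviation from the nominal collection time is permissible".
- **Extra samples (Protocol 9.5).** "A maximum of 3 samples may be collected at additional time points during the study if warranted", subject to agreement between investigator and sponsor. Dialysis is not mentioned.
- **Blood budget (Appendix 5).** The table of the "approximate number of venipunctures and blood volumes for all blood sampling" counts 13 PK samples.
- **Objectives and endpoints (Protocol section 4, SAP section 4).** PK parameters against controls, adverse events and antidrug antibodies. Removal by dialysis does not appear.
- **Analysis (Protocol 10.3.2.2, SAP 9.3.2).** "The 90% confidence interval of the ratio between each impaired renal function group versus the control group will be estimated". A supportive regression uses eGFR as the covariate. No dialysis clearance, fraction removed or pre/post ratio is defined.

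**The concern.** The rationale sets a question that nothing downstream answers. Measuring removal needs concentrations placed around a session, or drug measured at the dialyzer or in dialysate, together with an analysis of them. The plan specifies none of these.

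What it does estimate for Group 5 is total exposure relative to healthy controls. Two influences act on that ratio, possibly in opposite directions: lost renal function and removal by dialysis. A ratio near 1 would fit no removal, and it would fit removal offset by reduced clearance. Because Protocol 3.1 says the results will support dose recommendations in renal impairment, a report that followed 5.4 and drew a conclusion about dialysis would have no planned analysis behind it.

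**Working it through.** **1. Plan's own figure.** The documents give no number for dialysis removal. The only quantitative statement covering Group 5 is the precision of each group against control: 90% probability that the 90% CI half-width is within 0.29 (log scale), with 16 v 8 subjects and CV 32%. With SD = √ln(1 + 0.32²) = 0.312, that probability is 95.5% (22 df) or 99.4% (43 df), so the stated figure is conservative. The expected half-width is t × 0.312 × √(1/16 + 1/8) = 0.232 or 0.227. None of this concerns removal.

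**2. Sample count.** Ten scheduled plus three optional makes 13, exactly the Appendix 5 count. No separate dialysis samples are budgeted.

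**3. What the scheduled samples could show.** Half-life is about 5 days (Protocol 3.2), so k = ln 2/120 = 0.00578 per h.

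- Background decline over 24 h: 1 − e^(−24k) = 12.9%.
- Background decline over an assumed 4 h session: 1 − e^(−4k) = 2.3%.
- The ±10% window alone shifts concentration by 2.7% at 48 h (±4.8 h) and 5.4% at 96 h (±9.6 h) if nominal times are used; recorded actual times reduce this.
- Cmax occurs between 8 and 96 h (Protocol 3.2), so absorption may still be under way at the first session.

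Adjacent samples are 24 h apart from 24 to 96 h, and 72 h apart from 96 to 168 h. A session can fall between two of them, but much else changes over the same interval.

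**4. Confounding.** Simplest illustration: renal loss +25%, dialysis −20%, giving 1.25 × 0.80 = 1.00. A one-compartment model with three 4 h sessions a week from 24 h and an absorption half-life of 12 h (all assumed) gives:

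| Removed per session | AUC v no dialysis | Renal effect that cancels it (1/ratio) |
|---|---|---|
| 2% | 0.937 | 1.07 |
| 5% | 0.853 | 1.17 |
| 10% | 0.737 | 1.36 |
| 20% | 0.565 | 1.77 |

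Every row is compatible with an ESRD/control ratio of 1.

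**5. Exposure after session recording stops.** Under one compartment with first-order absorption, the share of AUC(0-∞) after 168 h is [ka·e^(−168k) − k·e^(−168ka)]/(ka − k), with ka set by tmax = ln(ka/k)/(ka − k).

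- tmax 8 h: ka = 0.582, share 38%.
- tmax 96 h: ka = 0.0171, share 54%.

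That part of the curve has no recorded session times, although PK sampling continues to Day 28 or later.

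**6. What paired samples would give.** For 8 subjects, the 90% CI half-width of the log post/pre ratio is t(0.95, 7) × s × √(2/8), with t = 1.895 and s the per-sample log SD. For an assumed per-sample CV of 5%, 10% or 15% this is 0.047, 0.094 or 0.141. It assumes the true ratio is the same in every subject and leaves out uncertainty in the reference change. Removal of a few percent per session could still go unseen; larger removal would be measured directly.

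**The case against.** The strongest reply is that the plan is not blind to dialysis. The 24 h rule puts the samples up to nominal 24 h before the first session, apart from the small window allowance. Subjects are resident to Day 5 with samples at 24, 48, 72 and 96 h, and actual sampling and session times are both recorded. Concentrations could be read against sessions, and Protocol 10.3 permits pooled population PK analysis. The SAP's example code, through the pdiff option, also outputs Group 5 against Group 4, whose members are not on dialysis.

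Much of this stands. A reader might infer that no dialysis information can be recovered at all; the documents do not support that. Nor do they support calling the membrane rule or the session times pointless: the membrane rule has a stated standardising purpose, and the session times could inform modelling. But none of this is a planned measure of removal. The pooled analysis is optional and names no dialysis covariate. Group 5 against Group 4 is a between-subject contrast, still confounded with residual renal function.

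A second reply is that 5.4 is a rationale, not an objective, and that it expects albumin binding to make a meaningful renal effect less likely. Both are fair. The first limits the seriousness of the point. The second is a prior expectation, and the sentence in 5.4 says the effect will be determined.

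**Conclusion.** The point holds in this form: as planned, the trial cannot determine the effect of dialysis on drug removal. No scheduled sample is set by reference to a session, no endpoint or analysis addresses removal, and the planned ratio cannot separate removal from lost renal function.

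A reader might go further and infer that the primary objective fails. It does not: each group's exposure against control, including ESRD subjects on dialysis, is estimated as intended. This is a recommended change, not a flaw in the main analysis.

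The 38–54% depends on the one-compartment form, a 120 h half-life and the documented tmax range. The cancellation table depends on an assumed session pattern and absorption rate and shows only that offsetting is possible. The design finding needs neither. Figure GPGG.2 (the Group 5 schematic) and the TFL shells could not be seen; a dialysis-linked sample or table appearing only there cannot be excluded, though the Schedule of Activities and Appendix 5 show no such sample.

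**What to change.** **Preferred: measure removal.**

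- In Protocol 9.5 and the Schedule of Activities, prespecify for Group 5 that two of the up to three additional PK samples are taken immediately before and immediately after the first post-dose dialysis session.
- Extend the recording of session times from Day 8 to the last PK sample.
- Add to SAP 9.3.2 a descriptive within-subject post/pre concentration ratio with 90% CI. Read it against the change expected over the same hours, taken from the subject's own off-dialysis samples or from the time-matched profile in the undialysed groups. State which reference is used and that absorption may be continuing.

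Cost: 2 × 3 mL = 6 mL of blood per Group 5 subject, within the sample count already allowed, plus one table. Appendix 5 needs correcting in any case: 13 × 3 mL is 39 mL, not the printed 26 mL, so the total becomes 175.5 + 13 = 188.5 mL and the rounded figure 190 mL, not 180 mL.

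**Fallback: align the wording.** Reword 5.4 to say that Group 5 estimates exposure in ESRD subjects on dialysis, and draw no conclusion about removal in the report. This requires no additional sampling or analysis, but leaves the removal question unanswered.
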